Exclusion Criteria	
A subject must NOT MEET ANY of the following exclusion criteria:
 
 1. Had previous lumbar spinal surgery (e.g., lumbar fusion, discectomy, laminectomy, laminotomy) 2. Has a medical, anatomical, and/or psychosocial condition that is contraindicated for commercially available Intellis™ SCS systems as determined by the Investigator 3. Has a diagnosed back condition with inflammatory causes of back pain (e.g., onset of severe pain with activity), serious spinal pathology and/or neurological disorders, as determined by the Investigator 4. Be concurrently participating in another clinical study 5. Has an existing active implanted device such as a pacemaker, another SCS unit, peripheral nerve stimulator, and/or drug delivery pump, etc. 6. Has a pain in other area(s) and/or medical condition requiring the regular use of significant pain medications that could interfere with accurate pain reporting, and/or confound evaluation of study endpoints, as determined by the Investigator 7. Has mechanical spine instability as determined by the Investigator 8. Has undergone, within 30 days prior to enrollment, an interventional procedure and/or surgery to treat back and/or leg pain, which is providing significant pain relief 9. Has unresolved major issues of secondary gain (e.g., social, financial, legal), as determined by the investigator

	
10. Be involved in an injury claim under current litigation or has a pending or approved worker's compensation claim
 
11. Be pregnant (determined by urine testing unless female subject is surgically sterile or post-menopausal. If female, sexually active, and childbearing age, subject must be willing to use a reliable form of birth control.)

Primary Endpoint	The primary efficacy endpoint is the percentage of randomized subjects who respond (a decrease in back pain VAS by at least 50% compared to baseline) to SCS therapy at 3 months (non-inferiority analysis). Subjects who do not have a successful Trial Phase are considered failures (non-responders) toward the primary endpoint.

Table of Contents

CLINICAL INVESTIGATIONAL PLAN	1
Study Synopsis.....	2
A. Purpose.....	7
A.1. Study Device	7
A.2. Purpose of the Investigation.....	7
A.3. Study Size	7
A.4. Duration of the Investigation	8
B. Protocol	8
B.1. Rationale for Study.....	8
B.2. Study Objectives	10
B.3. Selection of Study Population	10
B.3.1. Study Population	10
B.3.2. Inclusion Criteria.....	10

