The sample size estimate to determine primary endpoint is based on the primary objective of demonstrating non-inferiority of the test group to the control group at 3

months. Established methods were followed in determining the non-inferiority criteria and the related sample size estimate

- Test basis: Farrington-Manning binomial test for non-inferiority
- Estimated responder rate of 70% in the test group and 50% in the control group
- Significance level, alpha, of 0.05 one-sided
- Statistical power = approximately 90% or greater
- Non-inferiority margin of 10%
- Randomization: 1:1

Based on these assumptions, a minimum of 50 randomized and trialed subjects per treatment group (100 total) are required.

B.5.5.2 Overall Sample Size and Enrollment

Based on the primary endpoint requirement, a minimum of 50 subjects per treatment group are required (100 total). To account for a combined estimated attrition of 25% for subjects that do not complete the Trial Phase, and subjects that exit study before the 3-month primary endpoint visit, approximately 135 subjects would need to be randomized and trialed.

To account for 46% attrition prior to randomization (including subject ineligibility after signing the informed consent and subject dropout), it is estimated that a total of up to 250 subjects would need to be enrolled in the study.

B.5.6. Study Duration

This study is expected to last approximately 32 months. Enrollment of subjects is expected to last 18 months. Subjects who are expected to complete the study will commit to it for approximately 14 months. This consists of Baseline assessments, up to 10 days of trial stimulation, and 12 months of treatment following implantation and activation of the device.

B.5.7. Interim Administrative Analyses

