At the end of the Trial Phase, subjects will be assessed for pain intensity under optimal therapy parameters. Anterior-posterior (AP) and lateral X-ray imaging may be done at the end of the Trial Phase. The subject will be assessed for adverse events and medication usage.

Those who have a "successful Trial Phase" (defined as a 40% or greater pain reduction from Baseline in their back pain) will proceed to permanent implantation of a SCS system to evaluate the assigned therapy, and permanent implantation of the Intellis™ SCS system will be scheduled. A threshold of 40% for the Trial Phase was predetermined as the minimum pain reduction that warrants consideration of a permanent implant and an

opportunity to achieve a 50% pain reduction as defined in the Individual Subject Success criterion (see Section B.7.3.).)

Data from subjects who did not achieve 40% or greater pain reduction in back and do not receive permanent implantation will be carried forward toward the primary and secondary endpoints. These subjects will exit the study after being followed up for two weeks after explant of the leads to assess adverse events.

B.6.8. Permanent Device Implant (0-60 days from end of successful Trial Phase)

As described in section B.6.7, subjects who underwent a successful trial of the assigned SCS therapy and who agreed to continue into the next stage of the study will proceed to permanent implantation stage.

Permanent percutaneous leads will be placed in the epidural space at a vertebral level based on the subject's pain condition and pain pattern as described in the Intellis™ Physician Implant Manual. The INS will be implanted by a trained physician according to standard practice and following the Physician Implant Manual for the device. Anterior-posterior (AP) and lateral X-ray imaging will be obtained. Standard practice of a study site for prophylactic pre-surgery antibiotics and post-surgery pain medications will be followed). Subjects will be assessed for adverse events and medication usage.

B.6.9. Device Activation (0-14 days following Permanent Implant)

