B.7. Study Endpoints

B.7.1. Definition of Analysis Populations

- Modified Intent to Treat (mITT): All successfully randomized subjects who complete the Trial Phase.
- Intent-to-Treat (ITT): All successfully randomized subjects who met all the enrollment criteria.
- Per-Protocol (PP): All subjects who received a permanent device implant and contributed their data to the 3-month endpoint without any major protocol deviations or adverse events (that would render their data unevaluable).

The primary analysis of the primary and secondary endpoints will be performed on the mITT population. Supportive analyses will be performed for the Intent-to-Treat and Per-Protocol population.

For analyses incorporating crossover data (i.e. data gathered in the post 6-month periods), analyses will be based on the mITT population with treatment group defined by the treatment status at the corresponding time point to capture the impact of crossover. Additional sensitivity analyses censoring data post-crossover will be performed to examine the impact of crossover.

B.7.2. Effectiveness Assessment Definitions

- Primary Effectiveness Assessment: For subjects who have a successful Trial Phase and receive a permanent implant, the Primary Efficacy Assessment occurs at the follow up visit 3 months after Device Activation. For subjects who do not have a successful Trial Phase (based on subject's pain score) or subjects who do not want a permanent device implant due to insufficient pain relief (based on subject's discontinuation reason), the Primary Efficacy Assessment occurs at the end of the Trial Phase.

B.7.3. Primary Endpoint

Pain rating on the 10 cm Visual Analog Scale is considered the primary outcome measure. VAS is the most widely used outcome measure in assessing pain due to its documented reliability and validity, ease in administration, and minimal training requirements for the administrator.

- ***Individual Responder:*** A decrease in back pain VAS by at least 50% at 3 months after Permanent Device Activation as compared with Baseline. All subjects must be using the assigned programming parameters. If a subject is switched to a programming parameter that is not considered to be DTM-SCS nor Conventional SCS programming the subject will be counted as a non-responder for the following follow-up visit if one of the two following conditions exist:

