Missing data will be minimized by rigorous follow-up and investigator and site training. Additionally, for subjects who do not have a successful Trial Phase, results from the Trial Phase will be utilized for the primary endpoint as described in Section B.7.2. Effectiveness Assessment Definitions. Any other data will be imputed via Multiple Imputation. Additionally, sensitivity analyses for missing data will be performed. Unless otherwise specified, all other analyses will be based on the evaluable data with no imputation.

Details on imputation will be provided in a separate statistical analysis plan.

C. Risk Analysis

C.1. Description and Analysis of All Increased Risks to Subjects

Spinal Cord Stimulation (SCS) Risks:

DTM-SCS programming approach will be used with commercially available, FDA approved Intellis™ SCS system within approved indications for use. Anticipated potential adverse events resulting from the study are expected to be in line with adverse events already documented for SCS using a Standard programming approach.

There are known risks associated with the use of any SCS system. Known risks are associated with the implant procedure, the stimulation, the implanted device (not associated with stimulation) and external devices such as the charger and remote control. These are typical of commercial SCS systems. Subjects will be informed of these anticipated risks in the study consent process.

Risks of Surgery

Implanting a neurostimulation system has risks similar to spinal procedures, including spinal fluid leak (spinal fluid collection under the skin), headaches, swelling, bruising, bleeding, infection, or paralysis.

Subjects on anticoagulation therapy may be at higher risk for problems after surgery such as hematomas that could result in paralysis.

Spinal Cord Stimulation Risks

The implantation of a spinal cord stimulation system involves risks that are similar to other spinal procedures. In addition to those normally associated with surgery, implantation or use of a neurostimulation system includes, but is not limited to the following risks:

- Allergic or immune system response to the implanted materials
- Infection
- Lead or neurostimulator erosion through the skin or migration
- Leakage of cerebrospinal fluid
- Loss of pain relief may return patients to their underlying pain condition
- Persistent pain at the neurostimulator site

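### The primary endpoint is defined on all randomized subjects but tested on those who finish the Trial Phase, and failure-type exits before month 3 default to multiple imputation

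*Combined protocol and SAP*

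**What the plan says.** **Endpoint (synopsis, Primary Endpoint).** "The primary efficacy endpoint is the percentage of randomized subjects who respond" at 3 months. The next sentence reads: "Subjects who do not have a successful Trial Phase are considered failures (non-responders) toward the primary endpoint".

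**Analysis set (B.7.1).** "Modified Intent to Treat (mITT): All successfully randomized subjects who complete the Trial Phase". Then: "The primary analysis of the primary and secondary endpoints will be performed on the mITT population". ITT and per-protocol analyses are supportive. A successful Trial Phase is defined (back pain reduced by 40% or more; B.6.1 and B.6.7). Completing the Trial Phase is not.

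**Trial failures.** B.6.7: "Data from subjects who did not achieve 40% or greater pain reduction in back and do not receive permanent implantation will be carried forward". This covers the primary endpoint as well as the secondary ones. B.7.2 sets the primary assessment at the end of the trial for subjects whose pain score fails the threshold and for "subjects who do not want a permanent device implant due to insufficient pain relief". For unsuccessful trials, B.9.2.4 confirms that "results from the Trial Phase will be utilized for the primary endpoint".

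**Exits.** B.5.5.2 allows 25% attrition for "subjects that do not complete the Trial Phase, and subjects that exit study before the 3-month primary endpoint visit". B.6.18 and B.6.19 foresee explant or withdrawal, including for an adverse event, and B.6.19 also considers withdrawal for unsatisfactory effectiveness. The reason is recorded on the Study Termination eCRF. B.9.2.4 sends all other missing data to multiple imputation, plans sensitivity analyses, and leaves the imputation details to a separate SAP.

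**Responder rule (B.7.3).** Subjects must be on their assigned programming. Time on programming that belongs to neither arm makes a subject a non-responder under stated conditions.

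**The concern.** Two groups of randomized subjects are affected.

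- **Exits during the Trial Phase** (at most 10 days) before an end-of-trial score, for instance after an adverse event. The synopsis makes them failures. B.7.1 can leave them out of numerator and denominator.
- **Exits between implant and month 3** for lack of effect or an adverse event. They stay in mITT, but neither B.7.2 nor B.7.3 says explicitly that they are non-responders. Their missing month-3 value is imputed, so a subject explanted for lack of effect could be credited with response. A subject who declines the implant for the same reason is instead assessed on the trial result.

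Study success rests on this one test (B.8.2), and subjects and sites know the assignment (B.5.4), so exit decisions are made with the arm known. Two analysts following the document could score the same early exit differently.

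**Working it through.** **1. The plan's own figures.** Inputs from B.5.5.1: Farrington-Manning test, 70% vs 50%, margin 10 points, one-sided 0.05, 1:1. The statistic is

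Z = (pT − pC + 0.10) / √[qT(1−qT)/nT + qC(1−qC)/nC],

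where qT and qC are the maximum-likelihood rates restricted to qT − qC = −0.10, and the test rejects at Z ≥ 1.645. Full binomial enumeration at 50 per arm gives power 92.7%, in line with the stated aim of about 90% or more. 100/(1 − 0.25) = 134, matching about 135 randomized. The sample size is not in dispute.

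**2. Classification side by side.**

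| Subject | Synopsis | B.7.1, B.7.2 and B.9.2.4 |
|---|---|---|
| Finishes trial, under 40% relief | Failure | In mITT, trial result used |
| Declines implant for insufficient relief | No specific rule | Assessed at end of trial |
| Leaves trial before an end-of-trial score | Failure | Can be absent from mITT |
| Explant or withdrawal before month 3 for lack of effect or adverse event | No specific rule | In mITT, multiply imputed |

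The last two rows carry the problem.

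**3. Effect of removing Trial Phase exits.** The documents give no exit rates by arm, so these are assumptions. True all-randomized rates are 40% test and 50% control (exactly at the margin), with 67 per arm (135/2, rounded down). Exits are non-responders, binomial in each arm, and removed, so the rate among those who stay is p/(1 − e). Exact enumeration of the same test:

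| Exits, test / control | Chance of false non-inferiority |
|---|---|
| none | 5.4% |
| 2% / 1% | 5.5% |
| 5% / 2% | 6.7% |
| 10% / 5% | 7.8% |
| 2% / 2% | 4.9% |
| 2% / 5% | 3.3% |

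Shift in the expected difference, against the 10-point margin:
- 5% / 2%: (0.40/0.95 − 0.40) − (0.50/0.98 − 0.50) = 0.0211 − 0.0102 = 1.1 points.
- 10% / 5%: (0.40/0.90 − 0.40) − (0.50/0.95 − 0.50) = 0.0444 − 0.0263 = 1.8 points.

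**4. Effect of imputing post-implant exits.** The imputation model is not in the documents, so two assumed models were simulated (40,000 runs, 30 imputations, Rubin's rules). This used a Wald test, whose no-exit baseline is 5.3%, so the results are not directly comparable with step 3.

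| Exits, test / control | Imputed at arm's observed rate | At half that rate |
|---|---|---|
| 2% / 1% | 5.5% | 5.2% |
| 5% / 2% | 6.9% | 5.6% |
| 10% / 5% | 7.4% | 5.9% |
| 5% / 10% | 2.1% | 3.2% |

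**5. Power if exits count as failures.** Rates 0.70(1 − eT) and 0.50(1 − eC), 67 per arm:
- 2% / 1%: 96.7%.
- 5% / 2%: 94.9%.
- 10% / 5%: 91.7%.
- 25% each (0.525 vs 0.375): 90.7%, against 92.7% if removed.
- 15% / 5% (0.595 vs 0.475): 83.3%.

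**6. The opposite risk.** Set the null among those who stay (40% vs 50%) and count exits as failures. The expected difference narrows: at 5% / 10% exits it is 0.40 × 0.95 − 0.50 × 0.90 = −7.0 points. Non-inferiority is then declared 6.0% of the time at 5% / 5%, 7.9% at 2% / 5% and 10.3% at 5% / 10%. Removing exits gives 5.1% to 5.2% in each case.

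**The case against.** **The denominator gap is thin.** The sample-size text speaks of randomized and trialed subjects and treats Trial Phase non-completers as attrition, which agrees with mITT. B.7.3 does not mention randomized subjects; only the synopsis does. The gap covers exits within a phase of at most 10 days, and an ITT analysis is planned. All of this stands as a limit on size. It does not remove the conflict: a sample-size allowance classifies nobody, and a supportive analysis does not define the primary result. Editing the synopsis instead would also restore consistency, but would leave the primary test on a subset formed after randomization in an open-label trial.

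**Post-implant exits do have a stated handling.** A reader might infer that the plan says nothing about them. It does: B.9.2.4 assigns multiple imputation, with sensitivity analyses. The assigned-programming sentence in B.7.3 can also be read as barring response after explant. The surviving point is narrower. The non-response rule is not explicit, and what imputation would do depends on a model the documents do not show.

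**Counting exits as failures is a choice of estimand.** Steps 3 and 4 set the null on all randomized subjects with exits as failures, so other handling looks biased by construction; step 6 reverses the picture. This is a fair objection. The answer is that the synopsis already makes this choice for the Trial Phase, and that the drawback in step 6 must be disclosed.

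**Conclusion.** The concern holds in this limited form. As written, the primary test can measure a different quantity from the stated endpoint, and a subject explanted for lack of effect could be credited with response. It should be corrected before data are seen.

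The size is small for small exits and can go either way, on assumed exit rates throughout. Exits weighted to the test arm mostly raise the chance of false non-inferiority against the all-randomized null; equal or control-heavy exits make the test conservative. The earlier trial's responder rates (80% vs 51%, B.1) suggest, if anything, more lack-of-effect exits in control.

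Two stronger readings are tempting and unsupported. Subjects who finish and fail the trial are not dropped: the synopsis, B.6.7, B.7.2 and B.9.2.4 all keep them. Nor do the documents show a large inflation of type I error, since they give no exit rates by arm. The case rests on matching the test to its endpoint, not on expected harm.

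**What to change.** 1. **Analysis set.** In B.7.1, make all randomized subjects the primary set, matching the synopsis, with mITT and per-protocol supportive. Count randomized subjects who leave the Trial Phase for insufficient relief or an adverse event as non-responders. Define completion of the Trial Phase, since mITT remains in use. ITT as now defined also requires that all entry criteria were met, so it differs from all randomized only for subjects randomized in error.
2. **Exits before month 3.** In B.7.3, count explant or withdrawal for lack of effect or an adverse event as non-response for the primary endpoint, using the reason on the Study Termination eCRF. In B.9.2.4, limit multiple imputation to other missing values. Keep the current imputation approach and a tipping-point analysis by arm as sensitivity analyses.

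**Cost.** Protocol and SAP wording; no new visits or data. Responder rates fall slightly in both arms. Power stays at about 90% or more in most cases examined, but drops to 83.3% if exits run 15% test to 5% control. Because counting equal or control-heavy exits as failures narrows the difference and can ease non-inferiority, the mITT and per-protocol results should be reported beside the primary one.

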Subjects will undergo a Trial Phase with the randomly assigned treatment group. The Trial Phase will last up to 10 days and in accordance to approved labeling. Percutaneous leads will be placed in the epidural space at a vertebral level based on the subject's pain condition and pain pattern as described in the Physician Implant Manual. Stimulation will be delivered from an external neurostimulator (ENS).

Anterior-posterior (AP) and lateral X-ray imaging will be done following lead implantation at the beginning of the Trial Phase. The subject should flex forward prior to the final AP and lateral X-ray imaging. Imaging may also be done when lead migration is suspected.

Stimulation therapy will be as follows for each study arm:

- For Conventional SCS: stimulation parameters in the 40-250 Hz frequency range will be trialed according to standard practice as described in the Intellis™ labeling/manuals
- For DTM-SCS: As with Conventional SCS programming stimulation parameters will be trialed according to standard practice as described in the Intellis™ labeling/manuals. Subjects will be given multiple program groups to try. Each DTM-SCS program group will have multiple parameters. The stimulation parameters will be within the specifications described in the Intellis™ labeling/manuals. Each DTM-SCS program group has at least two programs with different pulse rate in the 50 to 1,000 Hz range and each having a maximum pulse width of 1 ms. The subject will progress through each of the program groups until satisfactory pain relief has been reached. The subject will be able to adjust the amplitude of the signals as deemed needed to obtain pain relief. If sufficient pain relief is not achieved with the initial program group, the subject will be instructed to trial another DTM-SCS program group.

Adjustments to a program group may be made based on patient feedback following the trialing of a particular program group or set of stimulation parameters. The primary factor for assessing response to a given program group or stimulation parameters is the subject's self-reported pain relief. Adjustments to therapy will be attempted until at least 50% self-reported back pain reduction from baseline is achieved or until conclusion of the trial phase (no more than 10 days). Subjects will be assessed for adverse events and medication usage.

B.6.7. End of Trial Assessment

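### The plan gives conflicting primary outcomes for a subject who reaches at least 50% relief in the Trial Phase but declines the implant for insufficient pain relief

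*Combined protocol and SAP*

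**What the plan says.** **Timing (B.7.2).** Two groups without an implant are assessed early. The first is subjects whose trial was unsuccessful on the pain score. The second is "subjects who do not want a permanent device implant due to insufficient pain relief", classified by the reason given for discontinuing. For both, "the Primary Efficacy Assessment occurs at the end of the Trial Phase".

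**Responder definition (B.7.3).** "A decrease in back pain VAS by at least 50% at 3 months after Permanent Device Activation as compared with Baseline".

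**Failure rule (synopsis, Primary Endpoint).** "Subjects who do not have a successful Trial Phase are considered failures (non-responders) toward the primary endpoint". A successful trial is "defined as a 40% or greater pain reduction from Baseline in their back pain" (B.6.7).

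**Use of trial data (B.6.7, B.9.2.4).** B.6.7 carries data forward for subjects who fell short of 40% and were not implanted. B.9.2.4 uses trial results for the primary endpoint when the trial was unsuccessful, citing B.7.2, and sends the remaining missing data to multiple imputation. Imputation details are deferred to a separate SAP, which is not among the documents.

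**How the trial score arises (B.6.6, B.6.7).** "Adjustments to therapy will be attempted until at least 50% self-reported back pain reduction from baseline is achieved", or until the trial ends. At the end, "subjects will be assessed for pain intensity under optimal therapy parameters".

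**Population (B.7.1).** The primary analysis set (mITT) is randomized subjects who complete the Trial Phase, so decliners belong to it.

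**The concern.** The second group in B.7.2 adds something only for subjects with a successful trial, because anyone under 40% is already in the first group. B.6.8 also allows for refusal after success, since implantation is for those who agree to go on. The plan therefore expects some subjects with at least 40% relief to leave because relief was not enough, and no failure rule is written for them.

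For those at 50% or more, the timing rule combined with the responder threshold turns a rejection for lack of efficacy into a primary success. It does so on a score taken within 10 days of starting trial stimulation, in place of one at 3 months. The trial is open-label, so refusals may differ between arms, and any imbalance enters the non-inferiority comparison directly. Leaving the scoring unsettled also means that it could be chosen after arm-level results are known.

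**Working it through.** **1. Each rule applied by level of end-of-trial relief, for a subject not implanted because of insufficient relief**

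| Relief at end of trial | Synopsis failure rule | B.7.2 timing + 50% threshold | B.7.3 literally | B.9.2.4 literally |
|---|---|---|---|---|
| under 40% | non-responder | non-responder | non-responder | trial result, so non-responder |
| 40% to under 50% | silent | non-responder | non-responder | imputed |
| 50% or more | silent | **responder** | **non-responder** | **imputed** |

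The rules agree in the first row. In the second, B.7.2 and B.7.3 agree but B.9.2.4 would impute. In the third, there are three different outcomes. This is also the only row in which carrying the trial score back can create a responder.

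**2. The plan's own figure**

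Inputs from B.5.5.1: 70% test, 50% control, margin 10 points, one-sided alpha 0.05, Farrington-Manning test, 50 per arm.

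- Restricted estimates under a difference of -0.10: 0.5441 (test) and 0.6441 (control).
- Null SE = sqrt[(0.5441 × 0.4559 + 0.6441 × 0.3559)/50] = 0.0977.
- Alternative SE = sqrt[(0.70 × 0.30 + 0.50 × 0.50)/50] = 0.0959.
- Power = Φ[(0.20 + 0.10 - 1.645 × 0.0977)/0.0959] = Φ(1.452) = 92.7%. Exact binomial enumeration also gives 92.7%.

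This agrees with the stated power of about 90% or more. Allowing for 25% attrition, 100/0.75 = 133.3, so 134, against about 135 planned, or about 67 per arm.

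**3. Effect of one subject**

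1/50 = 2.0 points; 1/67 = 1.5 points. With 25/50 responders in control, the test needs 29/50 in the test arm, so a single reclassified subject can decide the result.

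**4. Effect on the one-sided error (assumed shares)**

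The documents give no count of such decliners, so a share q of an arm is assumed. True rates are set at the margin, 40% test and 50% control, with decliners correctly non-responders. Counting them as responders makes the rates 40% + q(test) and 50% + q(control). The error is the exact binomial probability that the Farrington-Manning statistic reaches 1.645.

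| q test | q control | Error, 50 per arm | Error, 67 per arm |
|---|---|---|---|
| 0 | 0 | 4.7% | 5.4% |
| 2% | 0 | 6.9% | 8.6% |
| 4% | 0 | 9.9% | 12.9% |
| 0 | 2% | 3.0% | 3.3% |
| 0 | 4% | 1.8% | 1.9% |
| 4% | 4% | 4.5% | 5.5% |

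At 50 per arm, 2% is one subject and 4% is two.

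**5. The imputation route**

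The imputation model is not in the documents. If, as an assumption, a decliner were imputed at the planned rate of the arm, the expected credit would be 0.70 × 2.0 = 1.4 points per test-arm subject and 0.50 × 2.0 = 1.0 point per control-arm subject (50 per arm). This route therefore credits partial success too.

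**The case against.** A reader might infer that the plan settles the matter and counts these subjects as responders. The documents do not support that. B.7.2 says when the assessment happens and assigns no outcome. B.7.3 defines a responder at 3 months after activation, the synopsis endpoint and the B.9.2.1 hypotheses also refer to 3 months, and a subject who is never implanted cannot meet that definition. B.9.2.4 limits the use of trial results to unsuccessful trials. This part of the objection stands: responder is one of three readings.

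The group is also likely to be small. A subject must report at least 50% relief under the best settings and still cite insufficient relief. The likelier decliners are those at 40% to under 50%, who are non-responders under both B.7.2 and B.7.3. That stands as well, although the case is not absurd: a fall from 10.0 to 5.0 cm is 50% and still leaves substantial pain.

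A reader might further infer that the rule favours the test arm. Nothing in the documents says which arm would have more refusals. An excess in control makes the test conservative, and equal shares change little. Nor is the trial score necessarily a temporary-lead score, since B.6.1 allows temporary or permanent leads.

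Two possible mitigations fall short. The Per-Protocol analysis requires an implant and so drops these subjects, but it drops trial failures too and is only supportive. The separate SAP is to supply imputation details, and B.9.2.4 promises sensitivity analyses for missing data. Whether this subject counts as missing at all is an endpoint definition, and it belongs in the protocol.

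**Conclusion.** The point holds as a conflict between sections, not as a settled misclassification. B.7.2, B.7.3 and B.9.2.4 give three outcomes for an mITT subject with at least 50% trial relief who declines the implant for insufficient relief, and neither the synopsis nor B.6.7 resolves it. It is more than a missing detail, because two of the three routes can credit a primary success to a subject who rejected the therapy for lack of efficacy.

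The per-subject size (2.0 or 1.5 points against a 10-point margin) is plain arithmetic. The error rates rest on assumed shares, on true rates of 40% and 50%, and on non-responder being the right classification. Direction depends on an imbalance between arms that the documents do not give. The sample size calculation is not in error on this point. The change should be made.

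**What to change.** State in B.7.2/B.7.3, and mirror in the synopsis and B.9.2.4: *Any mITT subject who does not receive the permanent implant because of insufficient pain relief is a non-responder for the primary endpoint, regardless of the end-of-trial VAS, and is not multiply imputed.* B.9.2.4 has to change too; otherwise its imputation clause would still contradict the new rule. Add a sensitivity analysis that rescores these subjects as responders and as imputed, and report their number by arm.

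The rule matches B.7.3 and the way trial failures are already scored. It needs no new data, because the reason for discontinuation is already recorded at early withdrawal (B.6.19).

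The cost is that responder rates may fall slightly. If the planned 70% and 50% had counted such subjects as responders, exact power at 50 per arm would go from 92.7% to 88.9% with 2% in the test arm only, to 95.0% with 2% in control only, and to 91.5% with 4% in both.
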